Currently used response assessment guidelines used such as RECIST 1.1 and WHO (for response assessment in systemic solid tumors) have consistently proven inadequate due to the unique anatomy of the brain, presence of the neuro vascular unit (also referred to as the blood brain barrier (BBB)), blood tumor barrier and heterogeneity of tumors like glioblastoma [2, 50-52] [39-42]. It is now well understood that enhancement seen in MRI represents just the area with disrupted BBB and does not represent the whole tumor. The lack of reliable imaging biomarkers for response assessment is a major limiting factor in the development of new and effective therapies for brain tumors [51]. Further, agents like steroids and bevacizumab that are frequently used for symptom management in brain tumors can significantly alter imaging and alter response assessment. This lead to the development of the consensus based Response Assessment in Neuro-Oncology Working Group (RANO) criteria [53]. Based on RANO, all radiographic progression after 12 weeks post radiation is considered disease progression. The rate of pseudoprogression diagnosed at any time after radiation ranges from 9.3-31% [46]. Furthermore, around 30% of all pseudoprogression occurred beyond the 12-week RANO cut off including 2 cases occurring over 6 months after chemoradiation [3].

Figure 1 shows a case where the patient fulfilled criteria for progressive disease by RANO at 3 months after radiation, but was shown to have pseudoprogression by low blood volume on ferumoxytol (an iron oxide nanoparticle blood pool contrast agent) imaging.

Ferumoxytol Imaging: Differentiating Pseudoprogression from True Progression

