Figure 4: Charts show survival of GBM patients according to $rCBV$ by using four cutoff values. Tumor $rCBV$ was measured by using ferumoxytol versus gadoteridol and gadoteridol with leakage correction (Gadoteridol LC). Kaplan-Meier survival curves show best survival prediction by using $rCBV$ values obtained with ferumoxytol ($P = .001$) when cutoff range is between 1.5 and 2.0, and the same result was achieved with gadoteridol LC with cutoff of 1.5. By using gadoteridol, survival prediction is similar but not statistically significant ($P = .079$) for all cutoff values. Colored areas indicate 95% CIs.

[figure not shown]

Figure 5: Brain imaging using ferumoxytol: (A) High resolution images showing intravascular iron. (B) Delayed enhancement 24 hours after ferumoxytol administration.

[figure not shown]
[figure not shown]
[figure not shown]

Figure 6. Comparison of steady-state-cerebral blood volume (SS-CBV) and dynamic susceptibility contrast (DSC)-CBV maps in a glioblastoma patient. (A) T1-weighted postgadoteridol scan describes the multifocal signal abnormalities. In corresponding slices, the SS-CBV (B) and DSC-CBV (C) maps show increased areas of CBV referring to highly vascular tumor areas. Note the mismatch between the most enhancing region (arrow) and the highest CBV values. Reprinted from Varallyay et al. (2013).

Another major problem with response assessment is the use of VEGF inhibitors like bevacizumab or corticosteroids. These agents can alter the neurovascular unit around the tumor and decrease contrast enhancement (pseudo-response) when measured by conventional response criteria. Bevacizumab has failed to show significant survival benefits but is frequently used as an anti-edema measure [67-69].

[figure not shown]
Our preliminary data suggests that use of bevacizumab may alter rCBV measurements in high grade gliomas. For the purpose of this study, a short course of up to 3 doses of bevacizumab may be allowed, when clinically indicated, as an anti-edema measure and will not be criteria for exclusion. Bevacizumab is preferred over steroids when studying immune-modulatory therapies, since use of steroids can potentially dampen the immune response and outcomes.

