8.0 RESPONSE ASSESSMENT, IMAGE PROCESSING AND BIOMARKERS

8.1 Definitions for Response assessment:

The study will use the following criteria for the assessment of brain lesions.

Complete response (CR): Complete disappearance of all enhancing abnormalities on clinical enhanced MRI scan (in the absence of gadolinium, ferumoxytol enhancement will be used). Some subjects will have a small but persistent enhancing abnormality on MRI related to biopsy or focal hemorrhage. It is often difficult to ascertain whether this represents a residual nidus of tumor or scar tissue. Adjunctive radiologic studies such as SPECT or PET as clinically indicated may be helpful, but often the nature of these abnormalities may only be determined by following the subject with serial scans. If this type of abnormality does not change or slowly involutes over time off therapy and corticosteroids, it is reasonable to categorize it as a CR.

Partial Response (PR): At least 50% decrease in the contrast enhancing lesion seen on MRI as compared to baseline imaging. In the event of multiple lesions, the determination of partial response will be based on the sum of the bi-dimensional measurements (greatest diameter x greatest perpendicular) across lesions AND no new sites of disease

Stable disease (SD): less than a PR but is not progressive disease.

Progressive disease (PD):

- **Suspected Radiographic Progression:** progression will be defined by a 20% increase in volume of enhancement compared to the best response on clinical standard of care MRI. At any time point if progression is suspected on the clinical scan, additional steady state ferumoxytol MRI will be performed within 7 days of the clinical scan. Progression will then be confirmed with a follow up scan in 4 weeks \pm 5 days with a clinical standard of care MRI scan and additional ferumoxytol scan.
- **Persistent Radiographic Progression:** sustained and evident progression greater than increase in volume of enhancement compared to best response on a follow up scan at least 4 weeks after the scan where progression was suspected as per RANO BM form arm 1 or RANO criteria for subjects in arm 2. In cases with persistent radiographic progression the date of initial scan when progression was suspected will be considered to be the date of progression.
- Appearance of any new lesion or site of disease in the brain during or at the end of therapy.

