For specificity, it will be calculated based on patients with pseudo-progression determined by either surgical results or follow-up scan. We assume that 40% of the subjects (n = 17) will develop pseudo-progression, then if we observe 15 subjects (lesions) for whom the pseudo-progression status is correctly identified by ferumoxytol MRI, the specificity will be 88% with a 95% CI between 64% and 99% (Table 13).

Number of lesions with pseudo-progression	Number of Lesions with pseudo-progression detected by Ferumoxytol MRI	Specificity	Exact 95% CI of Specificity
17	17	100%	80% to 100%
17	15	88%	64% to 99%
17	13	76%	50% to 93%
17	11	65%	38% to 86%

Table 13: Estimated specificity and 95% CI based on 17 patients.

Statistical Analysis

For arm 2, sensitivity, specificity, rate of adverse events (safety and tolerability) and the distribution of best responses will be analyzed using proportions and exact 95% confidence intervals. In the primary analysis of sensitivity and specificity, the cutoff for rCBV will be specified as 1.75 (<1.75 is pseudoprogression and ≥ 1.75 is progression). Analysis of sensitivity will be based on patients with surgical results, and specificity analysis will be based on patients with pseudo-progression determined based on surgical results or follow-up clinical scan, as detailed in the power and sample size calculation section. In secondary analysis, we will try other cutoff points for rCBV, and include all patients that will be confirmed with true progression through surgery or follow up imaging. Progression free survival and overall survival will be assessed using the Kaplan-Meier product limit estimates for all patients, taking censoring into account. For exploratory objectives, continuous variables will be summarized

using mean and standard deviation, or median and range based on the distribution of data. The categorical variables will be summarized using frequencies and proportions, with exact 95% CI as appropriate.

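### Best response and its duration are scored on enhancement alone, with no corticosteroid or bevacizumab condition, and Section 10 has no analysis that separates drug-induced responses

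*Combined protocol and SAP*

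**What the plan says.** **Response definitions (Section 8.1).** PR is "At least 50% decrease in the contrast enhancing lesion seen on MRI as compared to baseline imaging". The main CR route is "Complete disappearance of all enhancing abnormalities on clinical enhanced MRI scan". Corticosteroids appear once, in the CR exception for a small residual abnormality left by biopsy or haemorrhage, which may be called CR if it "does not change or slowly involutes over time off therapy and corticosteroids". Bevacizumab is not mentioned in 8.1. RANO is cited for Arm 2 only under persistent radiographic progression, not under CR or PR.

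**Progression reference (Section 8.1).** For suspected progression, "progression will be defined by a 20% increase in volume of enhancement compared to the best response on clinical standard of care MRI". Duration of best response ends at progression judged against the smallest measurement since treatment began.

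**What the protocol says about the drugs (Section 4.0).** It warns that "agents like steroids and bevacizumab that are frequently used for symptom management in brain tumors can significantly alter imaging and alter response assessment", and that these drugs can "decrease contrast enhancement (pseudo-response) when measured by conventional response criteria". It allows up to three bevacizumab doses to control edema and prefers bevacizumab to steroids. Section 5.2 admits subjects on up to 8 mg of dexamethasone a day, and Table 6 calls for corticosteroids for several immune-related events.

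**Planned safeguards (Section 4.0; repeated in 4.2).** Study MRI is to precede bevacizumab where possible. Imaging data from subjects with more than three doses are analysed separately. A separate analysis by bevacizumab and steroid dose is promised.

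**Analysis (Section 10).** For Arm 2, "the distribution of best responses will be analyzed using proportions and exact 95% confidence intervals". Neither drug is mentioned.

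**The concern.** The protocol describes the artefact, permits the drugs that cause it, and then uses a response rule that cannot tell it from tumour response. A scan taken on bevacizumab or on a raised steroid dose that shows half the baseline enhancement is a PR under 8.1. That PR enters the best-response proportions. The same scan can also supply the smallest measurement against which the end of the response is judged.

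Section 3.2 makes best response and its duration secondary objectives and says the pilot data will be used to size a larger study. A planner reading the response rate would have no means, from the Section 10 output, of seeing how much of it came from scans on these drugs.

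**Working it through.** **1. Does any safeguard change a classification?**

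- *MRI before bevacizumab.* This applies where possible and to the scan before the first dose. Clinical MRIs continue every 9 weeks, so later scans are exposed.
- *More than three doses analysed separately.* Subjects with one, two or three doses stay in the main count.
- *Analysis by dose.* This describes subgroups. A PR reached on the drug is still a PR in each of them.
- *Not evaluable (8.1).* This covers extra interventions on target lesions. It names neither drug.
- *Section 10.* None of the above is carried over.

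So a drug-induced fall that meets the threshold is counted.

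**2. Method check on the plan's own intervals.** The plan states no response rate to reproduce, so the exact (Clopper-Pearson) method was checked on its sensitivity and specificity tables. For x of n, the lower limit is the 2.5% quantile of Beta(x, n−x+1) and the upper limit is the 97.5% quantile of Beta(x+1, n−x).

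- 22/26 = 84.6%, CI 65.1 to 95.6. The plan prints 85%, 65 to 96.
- 15/17 = 88.2%, CI 63.6 to 98.5. The plan prints 88%, 64 to 99.

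Both agree.

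**3. Illustration at n = 43 (Section 10).** The count of four other responders and the number added are assumptions. The documents give neither. Each added responder moves the proportion by 1/43 = 2.3 percentage points.

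| Drug-induced responses added | Reported | Rate | Exact 95% CI |
|---|---|---|---|
| 0 | 4/43 | 9.3% | 2.6 to 22.1 |
| 2 | 6/43 | 14.0% | 5.3 to 27.9 |
| 4 | 8/43 | 18.6% | 8.4 to 33.4 |
| 6 | 10/43 | 23.3% | 11.8 to 38.6 |

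**4. The reference scan.** Suppose enhancement volume is 100 at baseline and 40 on a drug. A later 48 is 48/40 = 1.20, a 20% rise from best and so suspected progression, yet it is 52% below baseline. If PR is measured by volume, 40 is a PR and 48 still meets the PR threshold. That overlap exists for any best value below 50/1.2 = 41.7% of baseline.

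The single-lesion metric for PR is not stated; 8.1 names the bidimensional product only for multiple lesions. With shape unchanged, a volume ratio of 0.40 is a product ratio of 0.40^(2/3) = 0.543. That is a 46% fall and not a PR. The example therefore depends on the metric.

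**The case against.** The strongest reply has five parts.

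- **CR is not wholly unconditioned.** True: the residual-abnormality route requires the subject to be off therapy and corticosteroids. The main CR route and PR remain unconditioned.
- **The protocol already plans for these drugs.** It does, in three ways, and it caps the entry steroid dose at 8 mg of dexamethasone a day. These measures reduce exposure or describe it. They do not alter which scans count, and Section 10 omits them.
- **The size is assumed.** This stands. No usage rate, fall rate or responder count is in the documents. PR is also judged from baseline, so a lesion that grew before bevacizumab must fall to half its baseline size. Some subjects on these drugs will be genuine responders.
- **The trial is an uncontrolled, descriptive pilot.** Response cannot be attributed to pembrolizumab alone under any steroid rule, and CR and PR do not enter the sensitivity and specificity analyses. This limits the consequence. It does not remove it, because the response data are meant to inform a later trial.
- **Changing the reference scan would change patient management.** This also stands. The suspected-progression trigger leads to the extra ferumoxytol MRI and the four-week work-up, and persistent progression leads to stopping pembrolizumab and to surgical evaluation.

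A reader might go further and infer that a rebound after the drug is withdrawn counts as progression and so distorts progression-free survival (PFS). The documents do not support that. A 20% rise is only suspected progression. It must be sustained at a scan at least four weeks later, with RANO cited for Arm 2. If the lesion is stable or smaller at four weeks, 8.1 calls it pseudoprogression. Whether such a rebound would pass RANO cannot be checked from these documents.

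**Conclusion.** The point holds for the secondary endpoints of best response and duration of best response. Applied as written, 8.1 counts a drug-induced fall in enhancement as PR or CR, and nothing in Section 10 separates such responses. The direction for the response proportion is upward. The effect on duration can go either way, because a drug-lowered scan can both supply the response and set the reference that ends it.

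The size is unknown. The doubling from 4/43 to 8/43 shows sensitivity under assumed counts and does not estimate the bias. No sample-size or precision figure in the plan changes. For PFS, the documents support only a possible influence through the reference scan, which a sensitivity analysis can show.

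**What to change.** **In Section 10, for analysis only:**

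1. Make the main best-response and duration table count CR or PR only from scans where the corticosteroid dose is not above the subject's baseline dose and no bevacizumab was given within an interval that the investigators fix before analysis. State the category given to a subject whose only CR or PR scans do not qualify, for example the best category reached on qualifying scans.
2. Show the unrestricted 8.1 counts beside it, both with exact 95% intervals.
3. Carry over from Section 4.0 the separate analysis above three bevacizumab doses and the analysis by bevacizumab and steroid dose.
4. For PFS, add at most a sensitivity analysis flagging progressions whose best-response reference scan was taken on bevacizumab or a raised steroid dose.

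Leave the on-study trigger for suspected progression unchanged. Ask the sponsor to reconcile the best-response reference in 8.1 with what Section 4.0 says about these drugs, and to state the metric for PR in a single lesion.

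**Cost.** A short addition to Section 10, with no new visits, scans or patients. Section 7.17.1 already requires concomitant medication to be recorded up to 30 days after the last trial treatment, and the analysis promised in Section 4.0 already needs doses. For scans after that window, medication data may be thinner. The reported response rate may be lower, and some genuine responders on these drugs will not count in the main table. The unrestricted column keeps them visible.

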2.0 TRIAL DESIGN

This study will evaluate incidence, magnitude and timing of true vascular tumor progression, pseudoprogression and immune response to pembrolizumab in patients with primary brain tumors using ferumoxytol steady state MRI imaging.

Originally, the study had two arms:

ARM 1: Metastatic brain tumors - Metastatic melanoma

ARM 2: Primary brain tumors - Glioblastoma (GBM)

In December 2019, we decided to stop the enrollment to the melanoma arm and allocate the remaining 18 slots to the Glioblastoma arm – a total of 43 subjects will now be enrolled in the GBM arm.

Treatment

Subjects scheduled to receive standard of care stereotactic radiosurgery (SRS) for brain metastases in Arm 1 or standard of care chemoradiation (CRT) with temozolomide for GBM in Arm 2, are eligible. All subjects will receive pembrolizumab (200mg intravenous every 3 weeks) in addition to standard of care SRS or CRT in the respective arms, until toxicity, or persistent radiographic progression is confirmed, whichever comes first.

Imaging

All subjects will be scanned with clinical MRI at baseline prior to radiation, 4 weeks after the last day of radiation and every 9 weeks thereafter until completion or until taken off-study for

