7.4 Study procedures narrative

Due to the innate differences in the pathology, natural history and differences in current standard of care for primary and metastatic brain tumors this pilot study will have two arms:

ARM 1: Metastatic brain tumors - Melanoma

ARM 2: Primary brain tumor - Glioblastoma multiforme (GBM)

All subjects will receive standard of care treatment for their respective arms as described in section 7.6.

All subjects will receive pembrolizumab (200 mg IV every 3 weeks) starting on the first day of radiation until persistent radiographic progression is confirmed, in addition to standard of care for their respective arms. Clinical MRI scans will be performed to assess response to therapy. Clinical standard of care MRIs are done at baseline, 4 weeks after the last day of radiation and then every 9 weeks thereafter until suspected radiographic progression. Early follow up clinical standard of care MRI (and ferumoxytol steady state MRI, see below) will be performed 4 weeks from the date of MRI showing suspected radiographic progression to confirm persistent radiographic progression (all timepoints \pm 5 days). Patients with imaging evidence of suspected radiographic progression may continue with one additional cycle of pembrolizumab. The decision regarding continuation of pembrolizumab will be made by the principle investigator based on clinical findings that include (1) stable ECOG performance status with no more than 8mg of dexamethasone (or equivalent) a day; (2) absence of new or worsening symptoms not managed with steroids; and (3) absence of progressive tumor at critical anatomical sites (e.g., spinal cord compression) requiring urgent alternative medical intervention.

Additional ferumoxytol steady state MRIs will be done at baseline, 4 weeks after the last day of radiation, at suspected radiographic progression and within 4 weeks from suspected radiographic progression to confirm persistent radiographic progression (all timepoints \pm 5 days). During this follow up period, subjects will be followed with a clinical exam weekly to monitor for clinical stability.

When persistent radiographic progression is confirmed, subjects will be evaluated for a craniotomy with intent to complete resection and/or biopsy of the enhancing lesion, if this is thought to be the clinical standard of care.

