- **Confirmation of true progression:** For the purpose of this study, Histopathologic evidence of viable tumor cells in patients with persistent radiographic progression will be define to have confirmed true progression. True progression is confirmed by histopathology, Pembrolizumab will be stopped and patient swill be taken off-study.. Patients who refuse biopsy or biopsy is not deemed clinically necessary will be taken off study at persistent radiographic progression. However, they will be continued to be monitored with clinical MRI scan and until death.
- **Pseudoprogression (PsP):** for the purpose of this pilot study, PsP may be confirmed by imaging or by pathology.
 - PsP Imaging: stable or decrease in volume of enhancement at 4 weeks (\pm 5 days) after suspected radiographic progression.
 - PsP pathology: No viable tumor tissue is seen by histopathology evaluation on tissue obtained after confirmed radiographic progression by imaging.
- **Clinical progression:** Subjects may be removed from study if they experience symptomatic deterioration without radiographic evidence of disease progression.

Not evaluable (NE): Only relevant if any of the target lesions had additional interventions for clinical managements, patient is unable to get follow up scans or images are of poor quality.

Duration of Best Response: The duration of best response is measured from the time measurement criteria are met for SD, CR or PR (whichever is first recorded) until the first date that recurrent or PD is objectively documented (taking as reference for PD the smallest measurements recorded since the treatment started).

Progression free survival and overall survival will be calculated from the date of diagnosis to the date of confirmed progression or death, respectively. The date of diagnosis was used because the time between the date of diagnosis and the start of treatment or date of enrollment may vary due to subject variables or logistical issues based on radiation planning.

Systemic Lesions (only for Arm 1):

Measurements based on RECIST version 1.1 will be used to make a diagnosis of suspected systemic progression; it will be confirmed using irRC at follow-up.

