10.0 STATISTICAL ANALYSIS PLAN

Given the exploratory nature of this study, the statistical analyses will be descriptive in nature. For the primary and secondary objectives, sensitivity, specificity, rate of adverse event and distribution of best responses will be analyzed using proportions and exact 95% confidence intervals. Progression free survival and overall survival will be assessed using the Kaplan-Meier product limit estimates. Outcomes in the exploratory objectives will be summarized using descriptive statistics as appropriate; and associations between immunological parameters, PDL-1 expression, clinical responses, radiological responses and other variables will be explored using two sample tests or correlation measures, as appropriate.

Power and sample size calculation for Arm 1

The accrual to arm 1 is stopped with 2 patients. These 2 patients will be described separately and no further analysis will be done.

Power and sample size calculation for Arm 2

For arm 2, we will enroll 43 GBM patients. Here we roughly estimate the precision of sensitivity and specificity in the primary objective based on these 43 patients.

In subjects with GBM, we anticipate to have only one lesion/subject. We assume that all subjects will eventually have disease progression and due to dropout and inoperable cases, a total of $n = 32$ subjects will undergo surgery to provide histopathological data on disease progression. Further, we assume that 40% of the $n = 43$ subjects will develop pseudo-progression and be observed based on follow-up scan.

For sensitivity, further assume that out of the $n = 32$ subjects who will undergo surgery, 26 subjects will have true progression based on pathology (gold standard). Then based on $n = 26$,

if we observe 22 subjects (lesions) for whom the true progression is correctly identified by Ferumoxytol MRI, then the sensitivity will be 85% with a 95% CI between 65% and 96% (Table XX).

Number of subjects (lesions) with true progression	Number of subjects (lesions) whose true progression was detected by Ferumoxytol MRI	Sensitivity	Exact 95% CI of Sensitivity
26	26	100%	87% to 100%
26	24	92%	75% to 99.1%
26	22	85%	65% to 96%
26	20	77%	56% to 91%
26	18	69%	48% to 86%
26	16	62%	41% to 80%

Table 12: Estimated sensitivity and 95% CI based on 26 subjects (lesions).

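### Most of the specificity set rests on an imaging pseudoprogression label from a single 4-week scan, with no tolerance for stable and no check against later MRIs

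*Combined protocol and SAP*

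**What the plan says.** **The label.** Section 8.1 states that "PsP may be confirmed by imaging or by pathology". The imaging route is "stable or decrease in volume of enhancement at 4 weeks" (±5 days) after suspicion. Section 7.4 describes the same finding as a lesion that has not changed or has shrunk, and keeps the subject on pembrolizumab until a later persistent progression is confirmed.

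**The comparison.** For suspicion, "progression will be defined by a 20% increase in volume of enhancement compared to the best response on clinical standard of care MRI". Persistent progression is "sustained and evident progression greater than increase in volume of enhancement compared to best response on a follow up scan"; that sentence has no percentage of its own.

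**The analysis.** In section 10, primary sensitivity uses patients with surgical results, while "specificity analysis will be based on patients with pseudo-progression determined based on surgical results or follow-up clinical scan". The planning figures are 43 subjects, 32 operated, 26 with true progression on pathology, and 17 with pseudoprogression. The section also says: "We assume that all subjects will eventually have disease progression". A secondary analysis adds true progression confirmed by follow-up imaging, but does not say that anyone then leaves the specificity set.

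**Later scans.** Section 2.0 has clinical MRI "4 weeks after the last day of radiation and every 9 weeks thereafter until completion or until taken off-study for" progression or toxicity. Section 7.4 has "Clinical standard of care MRIs are done at baseline, 4 weeks after the last day of radiation and then every 9 weeks", but its sentence goes on to end that schedule at suspected progression. Footnote 5 in section 6.0 has no such limit. Section 7.4 also follows every subject with clinical MRI until death or loss to follow-up.

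**The concern.** The two sides of the primary analysis have unequal reference standards. True progression needs tissue; pseudoprogression can rest on one short-interval scan. Nothing requires the stability to last, sets a minimum later follow-up, or says what happens to the label if the lesion then grows.

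The protocol itself gives reasons for doubt. Section 4.0 says bevacizumab and corticosteroids can reduce enhancement without a tumour response, and allows up to 3 doses of bevacizumab. Section 4.3.1 describes serial scans as the way true and pseudoprogression are now told apart. Section 8.1, under complete response, makes a similar remark about residual enhancement.

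A true tumour labelled as pseudoprogression and correctly read as rCBV ≥1.75 is scored as an error of the test. Section 4.3.1 says the study will establish sensitivity and specificity and that larger trials will be designed from its data, so a distorted specificity would carry forward.

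**Working it through.** **1. The plan's own figures (section 10, Tables 12 and 13).** 0.40 × 43 = 17.2, so n = 17. Clopper-Pearson for 15/17 gives 88.2% (63.6% to 98.5%), matching the stated 88% (64% to 99%). For 22/26 it gives 84.6% (65.1% to 95.6%), matching 85% (65% to 96%). The other rows also reproduce to rounding.

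**2. How many subjects depend on the 4-week scan.** Operated without true progression: 32 − 26 = 6. At most these 6 can be pseudoprogression by pathology, so at least 17 − 6 = 11 of 17 (65%) rest on imaging. If the plan means that all 17 are identified on the follow-up scan, it is 17 of 17.

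**3. Effect of m mislabelled tumours among the 17.** The documents give no value for m; it is assumed. At the plan's illustrative specificity (15/17) and sensitivity (22/26):

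expected specificity = [(17 − m) × 15/17 + m × (1 − 22/26)] / 17

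| m | Expected specificity |
|---|---|
| 0 | 88.2% |
| 1 | 83.9% |
| 2 | 79.7% |
| 3 | 75.4% |

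The step is (15/17 − 4/26)/17 = (0.882 − 0.154)/17 = 0.043, or about 4.3 points per subject. The 4/26 term means that about 15% of mislabelled tumours would have rCBV <1.75 and count as correct. Over the sensitivity range of Table 12 (16/26 to 26/26), m = 3 gives 79.5% to 72.7%.

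**4. What a later scan could show.** Assume constant growth from the suspicious scan and a reader who accepts under 20% further growth as stable (section 8.1 gives no figure).

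| Growth per 4 weeks | At 9 weeks | At 13 weeks |
|---|---|---|
| 5% | +11.6% | +17.2% |
| 10% | +23.9% | +36.3% |
| 15% | +37.0% | +57.5% |

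For example, 1.10^(9/4) = 1.239 and 1.10^(13/4) = 1.363. One later scan exposes the moderate growers but not the slowest.

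**5. Cost in precision of leaving cases out.** If 2 of 17 are set aside, 15 × 15/17 = 13.2, so about 13/15 = 86.7% (59.5% to 98.3%).

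**The case against.** A reader might infer something stronger: that steadily growing tumour is systematically labelled pseudoprogression, because a lesion that gains 20% in 9 weeks gains only 1.2^(4/9) = 1.084, or 8.4%, in the next 4. The documents do not support this.

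- Section 7.4 asks for no change or regression, and 8.4% growth is neither.
- Section 8.1 measures growth against best response. On that scale the lesion is at 1.2 × 1.084 = 1.30, or +30%. Even the fastest grower that stays under 20% in 4 weeks (1.2^(9/4) = 1.507 per 9 weeks) is at 1.507 × 1.2 = 1.81, or +81%. Both point to persistent progression.
- Suspicion need not arise over exactly 9 weeks. Best response may be any earlier scan, and footnote 5 in section 6.0 allows more frequent MRIs.

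Other strong inferences also fail. That the label is final is read from silence, and later growth does start a new work-up. Nothing bars a subject who later progresses and has surgery from the sensitivity set. Mislabelled tumours are not all false positives.

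The plan also has partial safeguards. Section 4.0 promises a separate analysis by bevacizumab and steroid dose, though section 10 does not carry it over and it does not revisit the label. The trial is a descriptive pilot with no formal hypothesis (section 3.4), and 4.3 points is small beside an interval of 64% to 99%.

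Finally, since every subject is expected to progress, regrowth at a later scan does not disprove earlier pseudoprogression. Dropping such cases from the primary estimate could inflate specificity. This stands, and it is why the check belongs in a sensitivity analysis.

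**Conclusion.** The gap is real but limited. A single scan with an undefined tolerance supplies at least 11 of the 17 planned specificity subjects, and no rule tests whether the label lasts. The routes to error are true tumour with temporarily flat or reduced enhancement, and slow growth that a reader accepts as stable. Visible steady growth is not one of them on the plan's own wording.

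The direction is downward whenever sensitivity exceeds 1 − specificity, as it does in the plan's illustrations. The size is about 4.3 points per mislabelled subject at sensitivity 22/26 and specificity 15/17. The number mislabelled is unknown, and 1 to 3 is only a scenario. The primary estimate can stand as defined, but readers need to see how far it depends on the 4-week label.

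**What to change.** For analysis only, keep the 4-week label for primary specificity and add to section 10 a pre-specified sensitivity analysis:

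- Include pathology-confirmed pseudoprogression, plus imaging pseudoprogression still durable at the next scheduled clinical MRI. Durable means under 20% growth in enhancement volume from the suspicious scan and no viable tumour in any tissue from that site.
- Count episodes that fail, or that have no such scan, as indeterminate and not as true progression.
- Report specificity with indeterminate episodes included and excluded, each with an exact 95% CI, and list steroid and bevacizumab use for each episode.
- State that exclusion may favour specificity and widens the interval, for example 60% to 98% for 13/15 against 64% to 99% for 15/17.

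Section 8.1 should also state the tolerance and reference scan that readers apply when calling a lesion stable for the analysis label. Sections 2.0 and 6.0 must be reconciled with section 7.4 on whether 9-weekly MRIs continue after suspected progression, because the check relies on that scan.

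The cost is wording, a sensitivity result that arrives one scan later, and a somewhat wider interval in that analysis. No additional scan is needed if the 9-weekly schedule continues, and treatment decisions do not change.
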